5.4.2 Rescue Medications & Supportive Care

5.4.2.1 Supportive Care Guidelines

Patients should receive appropriate supportive care measures as deemed necessary by the treating site Investigator including but not limited to the items outlined below:

Pneumonitis:

• For **Grade 2 events**, treat with systemic corticosteroids (1-2 mg/kg/day of prednisone or equivalent).

- For Grade 3-4 events, bronchoscopy should be performed to exclude infectious etiologies before starting immunosuppression. Once infectious etiologies are excluded, immediately treat with intravenous steroids (1-2 mg/kg/day of prednisone or equivalent). If symptoms persist for more than 3-5 days, then begin infliximab 5 mg/kg. When symptoms improve to Grade 1 or less, steroid taper should be started and continued over no less than 4 weeks. Permanently discontinue pembrolizumab.
- When symptoms improve to Grade 1 or less, steroid taper should be started and continued over no less than 4 weeks. Permanently discontinue pembrolizumab.
- Add prophylactic antibiotics for opportunistic infections in the case of prolonged steroid administration.

Diarrhea/Colitis:

Subjects should be carefully monitored for signs and symptoms of enterocolitis (such as diarrhea, abdominal pain, blood or mucus in stool, with or without fever) and of bowel perforation (such as peritoneal signs and ileus).

- All subjects who experience diarrhea/colitis should be advised to drink liberal quantities of clear fluids. If sufficient oral fluid intake is not feasible, fluid and electrolytes should be substituted via IV infusion. For Grade 2 or higher diarrhea, consider GI consultation and endoscopy to confirm or rule out colitis.
- For **Grade 2 diarrhea/colitis**, administer oral corticosteroids (1-2 mg/kg/day prednisone or equivalent).
- For **Grade 3 or 4 diarrhea/colitis,** treat with intravenous steroids (1-2 mg/kg/day prednisone or equivalent) followed by high dose oral steroids. If grade 3-4 diarrhea persists for more than 3-5 days, then begin infliximab 5 mg/kg.
 - For grade 4 diarrhea/colitis, permanently discontinue pembrolizumab.
- When symptoms improve to Grade 1 or less, steroid taper should be started and continued over no less than 4 weeks.

Type 1 diabetes mellitus (if new onset, including diabetic ketoacidosis [DKA]) or ≥ Grade 3 Hyperglycemia, if associated with ketosis (ketonuria) or metabolic acidosis (DKA)

- For **T1DM** or **Grade 3-4** Hyperglycemia

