 - Insulin replacement therapy is recommended for Type I diabetes mellitus and for Grade 3-4 hyperglycemia associated with

metabolic acidosis or ketonuria.

• Evaluate patients with serum glucose and a metabolic panel, urine ketones, glycosylated hemoglobin, and C-peptide.

Hypophysitis:

- For **Grade 2** events, treat with corticosteroids (1-2 mg/kg/day prednisone or equivalent). When symptoms improve to Grade 1 or less, steroid taper should be started and continued over no less than 4 weeks. Replacement of appropriate hormones may be required as the steroid dose is tapered.
- For **Grade 3-4** events, treat with an initial dose of IV corticosteroids followed by oral corticosteroids. When symptoms improve to Grade 1 or less, steroid taper should be started and continued over no less than 4 weeks. Replacement of appropriate hormones may be required as the steroid dose is tapered.

Hyperthyroidism or Hypothyroidism:

Thyroid disorders can occur at any time during treatment. Monitor patients for changes in thyroid function (at the start of treatment, periodically during treatment, and as indicated based on clinical evaluation) and for clinical signs and symptoms of thyroid disorders.

- Grade 2 hyperthyroidism events (and Grade 2-4 hypothyroidism):
 - In hyperthyroidism, non-selective beta-blockers (e.g. propranolol) are suggested as initial therapy.
 - In hypothyroidism, thyroid hormone replacement therapy, with levothyroxine or liothyronine, is indicated per standard of care.
- Grade 3-4 hyperthyroidism
 - Treat with an initial dose of IV corticosteroid followed by oral corticosteroids (1-2 mg/kg/day prednisone or equivalent). When symptoms improve to Grade 1 or less, steroid taper should be started and continued over no less than 4 weeks. Replacement of appropriate hormones may be required as the steroid dose is tapered.
 - Permanently discontinue pembrolizumab for **Grade 4** hyperthyroidism.

Hepatic Adverse Events:

- For **Grade 2** events, monitor liver function tests more frequently until returned to baseline values (consider weekly).
 - Treat with IV or oral corticosteroids (0.5-1 mg/kg/day prednisone or equivalent)
- For Grade 3-4 events, treat with intravenous corticosteroids for 24 to

48 hours (1-2 mg/kg/day prednisone or equivalent. If grade 3-4 hepatitis persists for more than 3-5 days, then begin mycophenolate 1 g twice daily. Permanently discontinue pembrolizumab for AST or ALT > 5x ULN or total bilirubin >3x ULN.

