- When symptoms improve to Grade 1 or less, a steroid taper should be started and continued over no less than 4 weeks.
- **Renal Failure or Nephritis**:For **Grade 2** events, treat with corticosteroids (1-2 mg/kg/day prednisone or equivalent).
- For **Grade 3-4** events, treat with systemic corticosteroids (1-2 mg/kg/day prednisone or equivalent). Permanently discontinue pembrolizumab.
- When symptoms improve to Grade 1 or less, steroid taper should be started and continued over no less than 4 weeks.
- Management of Infusion Reactions: Signs and symptoms usually develop during or shortly after drug infusion and generally resolve completely within 24 hours of completion of infusion. For Grade 3-4 events, stop infusion and permanently discontinue pembrolizumab.

Table 2 below shows treatment guidelines for subjects who experience an infusion reaction associated with administration of pembrolizumab (MK-3475).

| NCI CTCAE Grade | Treatment | Premedication at subsequent dosing |
|---|---|--|
| Grade 1 Mild reaction; infusion interruption not indicated; intervention not indicated | Increase monitoring of vital signs as medically indicated until the subject is deemed medically stable in the opinion of the investigator. | None |
| Grade 2 Requires infusion interruption but responds promptly to symptomatic treatment (e.g., antihistamines, NSAIDS, narcotics, IV fluids); prophylactic medications indicated for <=24 hrs | Stop Infusion and monitor symptoms. Additional appropriate medical therapy may include but is not limited to: IV fluids Antihistamines NSAIDS Acetaminophen | Subject may be premedicated 1.5h (± 30 minutes) prior to infusion of pembrolizumab (MK- 3475) with: Diphenhydramine 50 mg |
| NCI CTCAE Grade | Treatment | Premedication at subsequent dosing |

Table 2: Infusion Reaction Treatment Guidelines

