| | Narcotics Increase monitoring of vital signs as medically indicated until the subject is deemed medically stable in the opinion of the investigator. If symptoms resolve within one hour of stopping drug infusion, the infusion may be restarted at 50% of the original infusion rate (e.g., from 100 mL/hr to 50 mL/hr). Otherwise dosing will be held until symptoms resolve and the subject should be premedicated for the next scheduled dose. Subjects who develop Grade 2 toxicity despite adequate premedication should be permanently discontinued from further trial treatment administration. | po (or equivalent dose of antihistamine). Acetaminophen 500-1000 mg po (or equivalent dose of antipyretic). |
|--|--|---|
| Grades 3 or 4 Grade 3: Prolonged (i.e., not rapidly responsive to symptomatic medication and/or brief interruption of infusion); recurrence of symptoms following initial improvement; hospitalization indicated for other clinical sequelae (e.g., renal impairment, pulmonary infiltrates) Grade 4: Life-threatening; pressor or ventilatory support indicated | Stop Infusion. Additional appropriate medical therapy may include but is not limited to: IV fluids Antihistamines NSAIDS Acetaminophen Narcotics Oxygen Pressors Corticosteroids Epinephrine Increase monitoring of vital signs as medically indicated until the subject is deemed medically stable in the opinion of the investigator. Hospitalization may be indicated. Subject is permanently discontinued from further trial treatment administration. | No subsequent dosing |

Appropriate resuscitation equipment should be available in the room and a physician readily available during the period of drug administration.

- Steven Johnson syndrome (SJS) and Toxic Epidermal Necrolysis (TEN):
 - For signs or symptoms of SJS or TEN, withhold pembrolizumab and refer the patient for specialized care for assessment and treatment.
 - If SJS or TEN is confirmed, permanently discontinue pembrolizumab.
- o Immune-mediated myocarditis management
 - For suspected immune-mediated myocarditis, ensure adequate evaluation to exclude other etiologies, and administer corticosteroids as appropriate.

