6. DOSING DELAYS/DOSE MODIFICATIONS

Dose reduction of pembrolizumab will not be permitted in individual patients.

6.1 Discontinuation of Therapy:

Therapy with pembrolizumab will be permanently discontinued for any of the following:

a. Severe or life-threatening adverse reactions, including, but not limited to, any of the following (SARC must be notified in the event of these AEs and final decision regarding treatment will be made after a discussion):

- Drug related grade 4 toxicity (non-hematologic or hematologic)
- Diarrhea with abdominal pain, fever, ileus, or peritoneal signs; increase in stool frequency (7 or more bowel movements over baseline), stool incontinence, need for intravenous hydration for more than 24 hours, gastrointestinal hemorrhage, and gastrointestinal perforation
- Aspartate aminotransferase (AST) or alanine aminotransferase (ALT) >5 times upper limit of normal. For patients with liver metastasis who entered the study with grade 2 elevation of AST/ALT, pembrolizumab will be permanently discontinued if AST/ALT increase ≥ 50% relative to baseline and lasting ≥ 1 week)
- Total serum bilirubin >3 times upper limit of normal
- Severe (i.e., CTCAE grade 3 or 4) motor or sensory neuropathy, Guillain-Barré syndrome, or myasthenia gravis or other neurologic symptoms that impact activity of daily living
- Severe immune-mediated reactions involving any other organs (e.g., nephritis, pneumonitis, pancreatitis, non-infectious myocarditis)
- Immune-mediated ocular disease that is unresponsive to topical immunosuppressive therapy
- Grade 4 infusion reaction

• Confirmed diagnosis of Stevens-Johnson Syndrome (SJS) or Toxic Epidermal Necrolysis (TEN)

b. Inability to reduce corticosteroid dose for immune-related adverse reactions to ≤ 10 mg prednisone or equivalent per day

c. New or worsening ophthalmologic disorders, including loss of visual acuity or visual field and evidence of retinopathy.

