6.2 Withholding/Resuming Therapy

Study therapy will be withheld for the following adverse reactions:

a. A drug-related clinically significant toxicity \geq Grade 2, with the exception of the adverse reactions listed under requirement of permanent discontinuation of study therapy.

b. Grade 2 fatigue does not require the withholding of pembrolizumab.

c. When toxicity resolves or improves to \leq grade 1, therapy with pembrolizumab will resume.

d. In case toxicity does not resolve or improve to \leq grade 1 within 12 weeks after last administration of pembrolizumab, study drug discontinuation should be considered after discussion with SARC and overall study PI. If SARC, study PI and Merck are in agreement, patients who still have grade 2 toxicity at 12 weeks may continue on study only if asymptomatic and controlled.

e. Two dosing delays due to toxicity will be permitted. In the event of a third occurrence of a toxicity, which would require dosing delay, study therapy will be discontinued permanently.

f. For signs or symptoms of SJS or TEN, withhold KEYTRUDA® and refer the patient for specialized care for assessment and treatment.

Dose modification and toxicity management for immune-related AEs associated with pembrolizumab

AEs associated with pembrolizumab exposure may represent an immunologic etiology. These immune-related AEs (irAEs) may occur shortly after the first dose or several months after the last dose of pembrolizumab treatment and may affect more than on body system simultaneously. Therefore, early recognition and initiation of treatment is critical to reduce complications. Based on existing clinical trial data, most irAEs were reversible and could be managed with interruptions of pembrolizumab, administration of corticosteroids and/or other supportive care.

For suspected irAEs, ensure adequate evaluation to confirm etiology or exclude other causes. Additional procedures or tests such as bronchoscopy, endoscopy, skin biopsy may be included as part of the evaluation. Based on the severity of irAEs, withhold or permanently discontinue pembrolizumab and administer corticosteroids. Dose modification and toxicity management guidelines for irAEs associated with pembrolizumab are provided in Table 4.

Table 4: Dose Modification and Toxicity Management Guidelines for Immune-related AEs Associated with Pembrolizumab

General instructions:

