- 1. Corticosteroid taper should be initiated upon AE improving to Grade 1 or less and continue to taper over at least 4 weeks.
- 2. For situations where pembrolizumab has been withheld, pembrolizumab can be resumed after AE has been reduced to Grade 1 or 0 and corticosteroid has been tapered. Pembrolizumab should be permanently discontinued if AE does not resolve within 12 weeks of last dose or corticosteroids cannot be reduced to ≤ 10 mg prednisone or equivalent per day within 12 weeks.
- **3.** For severe and life-threatening irAEs, IV corticosteroid should be initiated first followed by oral steroid. Other immunosuppressive treatment should be initiated if irAEs cannot be controlled by corticosteroids.

| Immune-related AEs | Toxicity grade or conditions (CTCAEv4.0) | Action taken to pembrolizumab | irAE management with corticosteroid and/or other therapies | Monitor and follow- up |
|-----------------------|--|----------------------------------|---|---|
| Pneumonitis | Grade 2 Grade 3 or 4, or recurrent Grade 2 | Withhold Permanently discontinue | • Administer corticosteroids (initial dose of 1-2 mg/kg prednisone or equivalent) followed by taper | Monitor participants for signs and symptoms of pneumonitis Evaluate participants with suspected pneumonitis with radiographic imaging and initiate corticosteroid treatment Add prophylactic antibiotics for opportunistic infections |
| Diarrhea / Colitis | Grade 2 or 3 | Withhold | • Administer corticosteroids (initial dose of 1-2 mg/kg prednisone or equivalent) followed by taper | • Monitor participants for signs and symptoms of enterocolitis (ie, diarrhea, |

| Immune-related AEs | Toxicity grade or conditions (CTCAEv4.0) | Action taken to pembrolizumab | irAE management with corticosteroid and/or other therapies | Monitor and follow- up |
|---|---|----------------------------------|---|--|
| | Grade 4 | Permanently discontinue | | abdominal pain, blood or mucus in stool with or without fever) and of bowel perforation (ie, peritoneal signs and ileus). Participants with ≥ Grade 2 diarrhea suspecting colitis should consider GI consultation and performing endoscopy to rule out colitis. Participants with diarrhea/colitis should be advised to drink liberal quantities of clear fluids. If sufficient oral fluid intake is not feasible, fluid and electrolytes should be substituted via IV infusion. |

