| AST / ALT elevation or Increased | Grade 2 | Withhold | Administer corticosteroids (initial dose of 0.5- 1 mg/kg prednisone or equivalent) followed by taper | • Monitor with liver function tests (consider |
| bilirubin | Grade 3 or 4 | Permanently discontinue | • Administer corticosteroids (initial dose of 1-2 mg/kg prednisone or equivalent) followed by taper | weekly or more frequently until liver enzyme value returned to baseline or is stable |
| Type 1 diabetes mellitus (T1DM) or Hyperglycemia | Newly onset T1DM or Grade 3 or 4 hyperglycemia associated with evidence of β-cell failure | Withhold | Initiate insulin replacement therapy for participants with T1DM Administer anti-hyperglycemic in participants with hyperglycemia | • Monitor participants for hyperglycemia or other signs and symptoms of diabetes. |
| Hypophysitis | Grade 2 | Withhold | | • Monitor for signs and symptoms of |

| Immune-related AEs | Toxicity grade or conditions (CTCAEv4.0) | Action taken to pembrolizumab | irAE management with corticosteroid and/or other therapies | Monitor and follow- up |
|-----------------------------|--|--|---|--|
| | Grade 3 or 4 | Withhold or permanently discontinue ¹ | Administer corticosteroids and initiate hormonal replacements as clinically indicated. | hypophysitis (including hypopituitarism and adrenal insufficiency) |
| Hyperthyroidism | Grade 2 | Continue | • Treat with non-selective beta- blockers (eg, propranolol) or thionamides as appropriate | Monitor for signs and symptoms of thyroid |
| | Grade 3 or 4 | Withhold or permanently discontinue ¹ | | disorders. |
| Hypothyroidism | Grade 2-4 | Continue | • Initiate thyroid replacement hormones (eg, levothyroxine or liothyroinine) per standard of care | Monitor for signs and symptoms of thyroid disorders. |
| Nephritis and Renal | Grade 2 | Withhold | Administer corticosteroids (prednisone 1-2 mg/kg or | • Monitor changes of renal function |
| dysfunction | Grade 3 or 4 | Permanently discontinue | equivalent) followed by taper. | |
| Myocarditis | Grade 1 or 2 | Withhold | Based on severity of AE administer corticosteroids | • Ensure adequate evaluation to |
| | Grade 3 or 4 | Permanently discontinue | | confirm etiology and/or exclude other causes |
| All other immune-related | Intolerable/ persistent Grade 2 | Withhold | • Based on type and severity of AE administer corticosteroids | • Ensure adequate evaluation to |

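### Sections 5.4.2.1, 6.1/6.2, Table 4 and Table 5 do not give one consistent stopping rule for grade 4 hyperthyroidism, a first grade 2 pneumonitis and a grade 3 infusion reaction

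*Combined protocol and SAP*

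**What the plan says.** Stopping rules appear in the supportive care text of Section 5.4.2.1 (with Table 2), in the lists of Sections 6.1 and 6.2, and in Tables 4 and 5, which follow Section 6.2.

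- **Hyperthyroidism.** Section 5.4.2.1: "Permanently discontinue pembrolizumab for Grade 4 hyperthyroidism". Table 4 has a single row for grades 3 and 4, with the action "Withhold or permanently discontinue". The note under Table 4 allows resumption after a grade 3 or 4 immune-related endocrinopathy for which the drug was withheld, once the event is at grade 2 or lower and controlled. Section 6.1 separately lists any drug-related grade 4 toxicity as a reason to stop permanently.
- **Pneumonitis.** Section 5.4.2.1 has a grade 2 bullet (steroids only), a grade 3-4 bullet ending in permanent discontinuation, and then a separate bullet with no grade: "When symptoms improve to Grade 1 or less, steroid taper should be started and continued over no less than 4 weeks. Permanently discontinue pembrolizumab". Table 4 pairs grades and actions as "Grade 2 Grade 3 or 4, or recurrent Grade 2 | Withhold Permanently discontinue". Its general instructions let treatment resume once the event is down to grade 0 or 1 and steroids are tapered.
- **Infusion reaction.** Section 5.4.2.1: "For Grade 3-4 events, stop infusion and permanently discontinue pembrolizumab". Table 2, for grades 3 or 4: "Subject is permanently discontinued from further trial treatment administration". Table 5 likewise allows no further dosing at grades 3 or 4. The Section 6.1 list names "Grade 4 infusion reaction" and does not mention grade 3. Section 6.2a withholds for clinically significant drug-related toxicity of grade 2 or more, "with the exception of the adverse reactions listed under requirement of permanent discontinuation of study therapy", and 6.2c resumes treatment at grade 1 or less.

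**The concern.** A site managing one of these events can find two different answers in the protocol, depending on the page it opens. The issue is whether a patient is dosed again, so it bears first on safety, most plainly for re-exposure after an infusion reaction. It also bears on conduct. About 10 sites take part (Section 12.1.3), and like patients could be handled differently from one site to the next.

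There is a possible link to the primary endpoint. Under Section 2.17, response scans run until progression or the end of treatment. Under Section 11.1.4.4, best response depends on confirmation at a later time point. Whether a patient stays on treatment can therefore decide whether a later scheduled scan takes place.

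**Working it through.** The plan gives no figure on this point and no arithmetic applies. The check sets the passages side by side for each event.

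| Event | 5.4.2.1 (with Table 2) | 6.1 | 6.2a with 6.2c | Table 4 or Table 5 |
|---|---|---|---|---|
| Grade 4 hyperthyroidism | Stop permanently | Stop permanently (any drug-related grade 4), final decision after discussion | Not reached, since listed in 6.1 | Table 4: withhold or stop; note allows resumption |
| First grade 2 pneumonitis | Stop permanently, if the ungraded bullet is taken literally | Pneumonitis listed only when severe | Withhold, then resume | Table 4: withhold; resumption allowed |
| Grade 3 infusion reaction | Stop permanently (text and Table 2) | List is open-ended but names grade 4 only | Withhold, then resume, if grade 3 counts as unlisted | Table 5: stop permanently |

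**Grade 4 hyperthyroidism.** Section 5.4.2.1 and Section 6.1 agree, and Table 4 with its note is the odd one out. What two passages require, Table 4 makes one of two options. A site that stops permanently satisfies all of them. A site that withholds and later resumes satisfies Table 4 but not Section 5.4.2.1.

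**First grade 2 pneumonitis.** Within Section 6 the passages agree: Table 4 withholds, and so does 6.2a. The conflict comes from the ungraded bullet in Section 5.4.2.1, which has two possible readings.

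1. It is a duplicate. It repeats the last two sentences of the grade 3-4 bullet directly above it, and the grade 2 bullet says nothing about stopping.
2. It applies to every grade. The grade 3-4 bullet already carries the same sentences, so the separate bullet adds something only for grade 2. The colitis and nephritis lists in the same section also close with an ungraded taper bullet that reads as covering the grades above it.

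The text does not settle which was meant. On the second reading it contradicts Table 4.

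**Grade 3 infusion reaction.** Three event-specific instructions agree: the Section 5.4.2.1 text, Table 2 and Table 5. The loose end is the Section 6.1 bullet. Drug-related grade 4 toxicity is already the first item in that list, so naming grade 4 infusion reactions again invites the inference that grade 3 was left out on purpose. Because 6.2a turns on what is listed for permanent discontinuation, a reader who draws that inference arrives at withhold and resume.

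**The case against.** A reader might infer that Section 5.4.2.1 stands on one side and Section 6 on the other. The table shows otherwise. Table 5 agrees with Section 5.4.2.1 on infusion reactions, and Section 6.1 agrees with it on grade 4 hyperthyroidism. Only for pneumonitis does Section 6 as a whole differ from a passage in Section 5.4.2.1.

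A reader might also infer that the protocol directs re-dosing after a grade 3 infusion reaction. It does not. Section 6.1a covers severe reactions in general and says its list is not exhaustive, and its neuropathy item glosses severe as grade 3 or 4. To reach re-dosing, a site would have to treat that list as complete and set aside three specific instructions. This part of the defence stands: what remains is an under-inclusive bullet that leaves room for a wrong turn.

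On pneumonitis, duplication is a plausible explanation, but an editing slip in operative text still needs correcting. On hyperthyroidism, Table 4 does permit permanent discontinuation, so calling the passages flatly incompatible would be too strong. The row also carries a footnote marker with no matching number in the text available, so part of its content may have been lost. The note that can be read applies only where withholding is required. Even so, Table 4 leaves grade 4 looser than Section 5.4.2.1 does.

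There are safeguards. Section 6.1a requires notice to SARC and a discussion before the final decision, and Section 12.2 provides biweekly calls that cover toxicities. These reduce divergence between sites. They do not make the text consistent, and a site that follows Table 4 or 6.2 may not regard the event as one that triggers the 6.1a discussion.

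**Conclusion.** The point holds in a limited form: for these three events the protocol does not state one consistent stopping rule. The strength of the conflict differs by event. It is clearest for grade 4 hyperthyroidism, where a required stop in two places meets a permitted resumption in a third. For a first grade 2 pneumonitis it depends on reading the ungraded bullet literally. It is weakest for a grade 3 infusion reaction, where it needs a strained reading of Sections 6.1 and 6.2.

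Its size cannot be put as a number, because the documents give no frequency for any of the three events. It would be a further step to infer that the response rate or the operating characteristics in Section 13.1 are affected, and the documents do not support that step. Stopping treatment does not by itself make a patient non-evaluable under Section 11.1.1, and Section 10.3 provides a disease evaluation off treatment. No effect on the response rate, power or type I error is shown. The case for acting rests on patient safety and uniform handling across sites. No view is taken here on which clinical rule is right.

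**What to change.** Reconcile Section 5.4.2.1 (with Table 2), Sections 6.1 and 6.2, Table 4 with its note, and Table 5, so that each of the three events has one rule. Specifically:

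- settle what applies to grade 4 hyperthyroidism, and make the merged grade 3-4 row of Table 4 and its note agree with Sections 5.4.2.1 and 6.1;
- decide whether the ungraded pneumonitis bullet is a duplicate, then remove it or give it a grade so that it matches Table 4;
- make the infusion-reaction item in Section 6.1 and the carve-out in 6.2a agree with Tables 2 and 5.

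Keep each rule in one table and have the other sections refer to it. The medical lead decides the rule in each case. The cost is an amendment to the protocol wording and a memo to sites. No sample size or analysis changes.
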